13.4.1.2 Primary Efficacy Outcome Measure

The spontaneous ABR will be assumed to have a negative binomial distribution, and the mean ABR (95% CI) will be estimated using a general estimating equation (GEE) model framework (with a logarithmic link function which is the default for the negative binomial distribution) with treatment regimen as a fixed effect, subject effect as a random effect, age at baseline as a continuous covariate, and the logarithm of follow-up time (in years) as an offset.

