#### 5.8 Statistical Tests

The default significance level is to be 5%; confidence intervals are to be 95% and all tests are to be two-sided, unless otherwise specified in the description of the particular analyses.

P-values obtained from statistical inference tests are to be presented using four decimal places. P-values smaller than 0.0001, are to be presented as "<0.0001" and p-values

larger than 0.9999, but les than 1, are to be presented as ">0.9999". A p-value of exactly 1 is to be presented as "1.0000".

Unless otherwise specified the default summary statistics for quantitative variables are to be as follows:

- The number of subjects in each category (n).
- Mean
- Standard deviation (SD).
- First quartile (Q1).
- Median.
- Third quartile (Q3).
- Inter quartile range (IQR) calculated as Q3 Q1.
- Minimum.
- Maximum.
- The number of subjects (n) with missing or unavailable results for quantitative variables is to be presented as "Not reported" where applicable. A "Not reported" category is only to be presented should there be unavailable results. No distinction based on the reason for unavailable results are to be made in any presentations.

If the original data has N decimal places (as derived from the raw data) (i.e., decimal precision [N]) then the summary statistics are to contain the following decimal places (with a maximum of three decimals, unless data warrants the use of more decimals):

- Minimum and maximum: N.
- Mean, median, Q1, Q3 and IQR: N+1.
- Standard deviation: N+2.

For qualitative variables the number (n) and percentage (%) of subjects in each category are to be the default summary presentation. Unless otherwise specified, percentages are to be calculated relative to the total number of subjects in the relevant analysis set as described in the latest version of the Output Templates. In the event of unavailable assessments a "Not reported" category is to be presented. A "Not reported" category is only to be presented if applicable. The "Not reported" category is to be presented with a percentage so that the sum of the percentages of all categories, including the "Not reported" category, totals 100%. No distinction based on the reason for unavailable results are to be made in any presentations.

All values are to be rounded using the SAS® function ROUND. All computed percentages are to be presented using one decimal place.

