- A bleed is considered to be a minor bleed if the severity is indicated as "Mild" or "Minor".
- A bleed is considered to be a weekday bleed if the bleed occurred on a Monday, Tuesday, Wednesday, Thursday or Friday.
- A bleed is considered to be a weekend bleed if the bleed occurred on a Saturday or Sunday.
- A bleed is considered to be a morning bleed if the bleed occurred between 04:00 and 11:59.
- A bleed is considered to be an afternoon bleed if the bleed occurred between 12:00 to 17:59.
- A bleed is considered to be a night bleed if the bleed occurred between 18:00 and 03:59.
- A bleed is considered to have occurred at an unknown time if the time of a bleed is not available.
- Time since last prophylactic infusion in hours is to be derived as:
  - $Time(h) = Date/Time\ of\ Bleed\ Start\ Date/Time\ of\ Infusion$  where the start date/time of infusion refers to the last prophylactic infusion received (other than to treat a bleed) prior to the start of the bleed. Time since last prophylactic dose is to be categorized as:
    - $\circ$  <24 hours.

```
24 - <48 hours.

48 - <72 hours.

72 - <96 hours.

>96 hours.
```

• Time since previous bleed are only to be determine if a subject had multiple bleeds and is to be derived as:

```
Time(months)
= (Date/Time \ of \ Current \ Bleed
- Date/Time \ of \ Previous \ Bleed)/365.2425 \times 12
```

- A bleed is considered to be treated with BAX 855 if at least one infusion linked to the particular bleed is present in the *Study Infusion* eCRF panels. Infusions to "Maintain Hemostasis" are not to be summarized as part of treatment for bleeding episodes.
- The number of bleeds per subject overall and by location (target joint, non-target joint, joint and non-joint), causality (spontaneous/unknown and injury), severity (mild, moderate and severe) and timing (weekends, weekdays, morning, evening and afternoon) are to be determined as the count of unique bleeds in each category a subject had during the observation period.
- Annualized bleeding rate (ABR) is to be derived for each treatment regimen the subject had during the study as:

$$ABR = \frac{Number\ of\ unique\ bleeds}{OPE\ (years)\ for\ treatment\ regimen}$$

The ABR is to be analyzed using a generalized linear model fitting a negative binomial distribution with logarithmic link function. Only subjects that have 100 or more EDs are to be included in the models, where total EDs are derived as in Section 6.7: Extent of Exposure.

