The model is to be analyzed separately for each of the every 5 days and every 7 days treatment regimen. Baseline age and ABR as continuous covariate and the logarithm of the OPE in years, specific to each treatment regimen, as an offset, is to be included in the model. The following SAS® code is to be used to perform the analysis:

```
PROC GENMOD DATA = <ds>;
   MODEL <bleds> = <baseline_age> <baseline_ABR> / DIST = NEGBIN
   OFFSET = <log_OPE> LINK = LOG;
   LSMEANS <regimen> / BYLEVEL OM CL;
   ODS OUTPUT LSMEANS = <outds>;
RUN;
QUIT;
```

where <ds> refers to the input dataset, <regimen> the particular treatment regimen time of bleed, <ble> the number of bleeds during the observation period, 
 baseline\_age> the age at baseline, 
 baseline\_ABR> the ABR at baseline and <log\_OPE> the logarithm of the OPE in years, specific to the treatment regimen. Point estimates and confidence intervals obtained from the generalized linear model are to be anti-logged prior to presentation.

The twice weekly regimen and PK-tailored regimen will be analyzed together (not separately as per above model) using a generalized estimating equation (GEE) model using the following SAS® code:

```
PROC GENMOD DATA = <ds>;
   CLASS <subject> <regimen>;
   MODEL <bleeds> = <regimen> <baseline_age> / DIST = NEGBIN
   OFFSET = <log_OPE> LINK = LOG;
   REPEATED SUBJECT = <subject> / CORR = EXCH;
   LSMEANS <regimen> / BYLEVEL OM CL;
   ODS OUTPUT LSMEANS = <outds>;
RUN;
```

where <ds>, <regimen>, <bleeds>, <baseline\_age> and <log\_OPE> is define the same as before and <subject> is the subject number.

For both models above, should the model not converge a poisson model will be fitted instead. Should the non-convergence be due to all bleeds equal to zero, the estimate will be presented as zero with no confidence interval.

The model results are to be presented on the FAS and PPAS for:

- The total ABR.
- Annualized joint bleeding rate.
- Annualized non-joint bleeding rate.
- Annualized target joint bleeding rate.
- Annualized non-target joint bleeding rate.
- Annualized injury related bleeding rate.
- Annualized spontaneous/unknown bleeding rate.
- Annualized severe bleeding rate.
- Annualized moderate bleeding rate.
- Annualized minor bleeding rate.
- Annualized weekday bleeding rate.

- Annualized weekend bleeding rate.
- Annualized morning bleeding rate.
- Annualized afternoon bleeding rate.
- Annualized night bleeding rate.
- Annualized bleeding rate at unknown time.

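### An all-zero bleed category is to be reported as 0 with no interval, so the printed result does not show how much follow-up lies behind it

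*SAP*

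**What the plan says.** SAP section 7.1 specifies negative binomial models with a log link for the annualized bleeding rate (ABR). The every-5-day and every-7-day regimens each have their own model: "The model is to be analyzed separately for each of the every 5 days and every 7 days treatment regimen". The twice-weekly and PK-tailored regimens share one generalized estimating equation (GEE) model. The observation period for efficacy (OPE) enters on the log scale: "the logarithm of the OPE in years, specific to each treatment regimen, as an offset". Only subjects with at least 100 exposure days are modelled.

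Two fallback rules cover both models. First, "should the model not converge a poisson model will be fitted instead". Second, if the failure arises because every count is zero, "the estimate will be presented as zero with no confidence interval". They apply to all 16 bleeding rates listed in that section, on the full and per-protocol analysis sets.

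No substitute limit appears elsewhere. The descriptive ABR summaries in section 7.1 specify no interval for the rate. SAP section 5.8 sets the general default ("confidence intervals are to be 95% and all tests are to be two-sided") but lets individual analyses specify otherwise. For the primary efficacy outcome, protocol section 13.4.1.2 says "the mean ABR (95% CI) will be estimated using a general estimating equation (GEE) model".

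**The concern.** Zero bleeds over a finite observation time is compatible with a rate above zero, and how far above depends on that time. A bare zero does not convey this. Two all-zero cells, one from a handful of subjects followed for three months and one from a large group followed for a year, would look the same in the table.

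The gap concerns the places where data may be thinnest. The 16 rates include severe, target-joint and unknown-time bleeds. The every-5-day and every-7-day regimens are kept only for subjects already on them before protocol amendment 4 (protocol section 8.7.3, footnote) and are modelled one at a time. The SAP also uses an exact method for another outcome that may be rare: the Clopper-Pearson interval for inhibitor development in section 8.3, which remains defined at zero events.

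**Working it through.** The documents give no figure on this point, so there is none to reproduce.

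**Inputs.** Confidence level 95%, two-sided (SAP 5.8). Poisson as the fallback distribution (SAP 7.1). Total OPE in years, T, obtained by summing the subject-level values that SAP 6.7 already derives overall and by regimen. Planned participation of about 3 to 12 months (SAP 6.1). The number of subjects per regimen and the person-years per regimen are not given, so every n and T below is an assumption.

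**Why the model gives no interval.** With all counts zero, the fitted log rate has no finite value. Test fits to all-zero counts failed under both Poisson and negative binomial (dispersion fixed at 1), so the Poisson fallback does not rescue this case.

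**Poisson upper limit.** With zero events in T person-years, the upper limit solves exp(−λT) = 0.025, so λ = −ln(0.025)/T = 3.689/T. The lower limit is 0.

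| Assumed person-years T | Upper limit, bleeds per year |
|---|---|
| 1.25 (5 subjects × 0.25 y) | 3.689/1.25 = 2.95 |
| 10 | 0.37 |
| 15 | 0.25 |
| 30 | 0.12 |
| 200 (200 subjects × 1 y) | 0.018 |

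The first and last rows differ by a factor of 200/1.25 = 160. Under the current rule both would print as 0 with nothing beside it.

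**Sensitivity to overdispersion.** The planned model is negative binomial. With dispersion k, n subjects and t years each, the probability that all counts are zero is (1 + kλt)^(−n/k). Setting this to 0.025 gives λ = (0.025^(−k/n) − 1)/(kt). For n = 10 and t = 0.5:

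- Poisson: 3.689/5 = 0.74
- k = 1: (1.446 − 1)/0.5 = 0.89
- k = 2: (2.091 − 1)/1 = 1.09
- k = 4: (4.374 − 1)/2 = 1.69

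For n = 100 and t = 0.5 the Poisson limit is 0.074, against 0.075 to 0.079 for k from 1 to 4. The understatement is material in small groups and negligible in large ones. All-zero data cannot estimate k.

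**A limit that needs no count distribution.** The Clopper-Pearson upper limit for the proportion of subjects with any bleed, at 0 of n, is 1 − 0.025^(1/n): 52.2% for n = 5, 30.8% for n = 10, 16.8% for n = 20 and 1.8% for n = 200.

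**The case against.** The rule is deliberate and prespecified. SAP section 5.8 allows an analysis to depart from the 95% default, and section 7.1 does so openly. A reader might infer that the SAP contradicts itself here; it does not.

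The proposed limit is exact only for a common Poisson rate, and Poisson is the fallback rather than the planned model: "The ABR is to be analyzed using a generalized linear model fitting a negative binomial distribution with logarithmic link function". In the 10-subject example the Poisson value is less than half the value at dispersion 4, and small groups are where the interval would be most wanted. It is also a crude rate. It would sit beside means adjusted for age, and for baseline ABR as well in the every-5-day and every-7-day models. These points stand. They call for a label and a caveat, not for an empty cell.

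The zero would not stand wholly alone either: section 7.1 adds descriptive ABR summaries and section 6.7 summarises exposure by regimen. That helps only in part, because those summaries are not restricted to the subjects with at least 100 exposure days who enter the model.

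Finally, the documents give no regimen sizes and no expected rates for rare bleed types. A reader might infer that all-zero cells will occur, or that the every-5-day and every-7-day groups are small. The documents support only that all-zero cells may occur and that the SAP provides for them.

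**Conclusion.** The point holds as a minor reporting gap. An all-zero category would be printed without the one figure that shows how much follow-up supports it, although that figure needs only a quantity the SAP already derives. Its size depends on assumed person-years: an upper limit of 0.37 bleeds per year at 10, 0.25 at 15 and 0.12 at 30, on the Poisson assumption, and higher in small groups if counts are overdispersed.

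A reader might go further and infer that the co-primary efficacy result could be reported without an interval. For the twice-weekly and PK-tailored regimens, the rule is triggered only if every spontaneous bleed count in the joint model is zero. That is very unlikely in a study planning 200 evaluable subjects. The realistic reach is sparse secondary categories and the two separately modelled regimens. The planned sample size does not depend on this rule, and the primary analysis is not in error.

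**What to change.** Replace the all-zero rule in SAP section 7.1 with text along these lines: If all counts are zero, the rate is presented as 0 with a two-sided 95% interval of 0 to 3.689 divided by total OPE in years. The interval is labelled as unadjusted and exact under a Poisson assumption, and is shown with the number of modelled subjects and their total OPE. A footnote states that the limit is too low in small groups if counts are overdispersed.

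Optionally, add the Clopper-Pearson upper limit for the proportion of subjects with any bleed, which uses the same kind of interval as section 8.3.

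The cost is one SAP sentence, a footnote and one line of code, with no new data and no effect on other results. The small downside is a crude, assumption-dependent figure beside covariate-adjusted means; the label deals with that.

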The spontaneous ABR will be assumed to have a negative binomial distribution, and the mean ABR (95% CI) will be estimated using a general estimating equation (GEE) model framework (with a logarithmic link function which is the default for the negative binomial distribution) with treatment regimen as a fixed effect, subject effect as a random effect, age at baseline as a continuous covariate, and the logarithm of follow-up time (in years) as an offset.

Analysis of Secondary Outcome Measures

Efficacy:

The total ABR (spontaneous and traumatic bleedings) will be estimated and described similarly as the primary efficacy outcome measure.

The efficacy of BAX 855 in the treatment of bleeds will be summarized. It includes overall hemostatic efficacy rating at 24 (± 2) hours after initiation of treatment and at resolution of bleed, number of BAX 855 infusions to control bleeding and total weight-adjusted dose per bleeding episode (excluding any infusions given to maintain hemostasis after the bleeding was controlled), and time interval between bleeding episodes.

Frequency tables will be prepared for the number of BAX 855 infusions required for the treatment of bleeding episodes. The median number of infusions (and nonparametric 95% CI) will be estimated.

Weight-adjusted consumption of BAX 855 for prophylaxis, treating bleeding episodes (excluding any infusions given to maintain hemostasis after the bleeding is controlled) and in total per subject will be summarized separately as average number of BAX 855 infusions and average weight-adjusted consumption of BAX 855 per month.

The average time interval between 2 consecutive bleeding episodes will be computed for each subject as the duration of the observation period divided by the number of bleeding episodes in the observation period. The median (95% CI) of those average time intervals between 2 bleeding episodes will be estimated.

Pharmacokinetics:

For subjects undergoing a pharmacokinetic (PK) assessment in this study, the following PK parameters for FVIII will be reported using descriptive statistics: area under the plasma concentration curve from 0 to infinity ($AUC_{0-\infty}$), half-life ($T_{1/2}$), mean residence time (MRT), total body clearance (CL), incremental recovery over time (IR), maximal plasma concentration (C_{max}), and volume of distribution at steady state (V_{ss}).

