8.3 Duration of Study Period(s) and Subject Participation

The overall duration of this continuation study is estimated to be approximately 4 years from study initiation (ie, first subject enrolled by signing informed consent) to study

ⁱⁱⁱ Except at visits 4 ± 1 , 8 ± 1 and 18 ± 2 weeks following baseline in those subjects receiving PK-tailored treatment regimen.

completion (ie, last subject last visit). Recruitment of transitioning subjects will continue until the last subject has completed any other BAX 855 study.

Each subject will participate in the study until a total of at least 100 EDs to BAX 855 has been achieved (accumulated across all BAX 855 studies in which each subject participated). Depending on the subject's BAX 855 exposure history and treatment regimen given, the planned duration of subject participation to reach the 100 EDs (from enrollment to subject completion) can vary from approximately 3 to 12 months. However, extension of the study duration for individual subjects beyond the 100 EDs may be granted.

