11.4 Time Intervals Between Bleeding Episodes

The time interval between bleeding episodes will be calculated based upon the date and time reported for each bleeding episode. The subject, the subject's caregiver, and/or investigator will determine when a bleeding episode has occurred (see Section 11.1 above).

11.5 Weight-Adjusted Consumption of BAX 855

Weight-adjusted consumption of BAX 855 will be determined based upon the amount of BAX 855 infused, as record in subject's diary and the subject's weight, as measured at the study site.

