13.4.2 Secondary Outcome Measures

13.4.2.1 Secondary Efficacy Outcome Measures

The total ABR (spontaneous and traumatic bleeding episodes) will be estimated and described similarly as the primary efficacy outcome measure.

The efficacy of BAX 855 in the treatment of bleeds will be summarized. It includes overall hemostatic efficacy rating at 24 (± 2) hours after initiation of treatment and at resolution of bleed, number of BAX 855 infusions to control bleeding and total weight-adjusted dose per bleeding episode (excluding any infusions given to maintain hemostasis after the bleeding was controlled), and time interval between bleeding episodes.

Frequency tables will be prepared for the number of BAX 855 infusions required for the treatment of bleeding episodes. The median number of infusions (and nonparametric 95% CI) will be estimated.

Weight-adjusted consumption of BAX 855 for prophylaxis, treating bleeding episodes (excluding any infusions given to maintain hemostasis after the bleeding is controlled) and in total per subject will be summarized separately as average number of BAX 855 infusions and average weight-adjusted consumption of BAX 855 per month.

The average time interval between 2 consecutive bleeding episodes will be computed for each subject as the duration of the observation period divided by the number of bleeding episodes in the observation period. The median (95% CI) of those average time intervals between 2 bleeding episodes will be estimated.

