A figure presenting results from the generalized linear model on the total ABR is to be presented for the FAS. Figures are also to be presented showing the number of bleeds within a specific time category since previous prophylactic infusion as well as bleeds overlaid with all treatments received during the study and binding antibodies on the FAS.

ABR for the above categories is to be presented descriptively for the FAS and PPAS. Descriptive statistics on the average duration between bleeding episodes for subjects with more than one bleeding episode and characteristics of bleeding episodes (including number of infusions to treat each bleed, total dose [IU] to treat each bleed, average dose per infusion to treat each bleed [IU/kg], efficacy rating, time since previous prophylactic dose [h] and severity of each bleed) are to be presented for the FAS and PPAS as well. Summaries for bleeding episodes are to be presented by age category, presence of target joints at screening and treatment regimen at time of bleed. Descriptive summaries on the number of infusions to treat a bleed are to include the 95% confidence interval on the median number of bleeds. The 95% confidence interval on the median will be determined using the distribution-free confidence interval for the 50th percentile from the SAS® UNIVARIATE procedure.

Information on bleeding episodes including the course of target joints and ultrasound information is to be listed for the SAS.

#### 7.2 Weight-adjusted Consumption of BAX 855

Weight-adjusted consumption of BAX 855 is discussed in Section 6.7 Extent of Exposure.

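### SAP 7.1 summarises time between bleeds only in subjects with two or more bleeds and asks for no confidence interval; this departs from Protocol 13.4.2.1 and is not declared in SAP 5.7

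*SAP*

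**What the plan says.** Both documents list time intervals between bleeding episodes as a secondary efficacy outcome (Protocol 8.4.2.1, SAP 3.1.2.1).

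- **Protocol 13.4.2.1**, repeated in the synopsis, computes a per-subject average "as the duration of the observation period divided by the number of bleeding episodes in the observation period". It then prescribes the statistic: "The median (95% CI) of those average time intervals between 2 bleeding episodes will be estimated". It sets no minimum of two bleeds.
- **Protocol 11.4** describes the same outcome differently: "The time interval between bleeding episodes will be calculated based upon the date and time reported for each bleeding episode". It gives no summary statistic and no population.
- **SAP 7.1** derives one between-bleed quantity, the time from the previous bleed to the current one in months: "Time since previous bleed are only to be determine if a subject had multiple bleeds". It then plans descriptive statistics on "average duration between bleeding episodes for subjects with more than one bleeding episode".
- **CI on a median in SAP 7.1.** The only such request concerns infusions per bleed: "Descriptive summaries on the number of infusions to treat a bleed are to include the 95% confidence interval on the median number of bleeds".
- **SAP 5.8** introduces its default list with "Unless otherwise specified the default summary statistics for quantitative variables are to be as follows". The list runs from n to the maximum and contains no CI.
- **SAP 5.7** declares two changes from the protocol: imputation of certain missing data, and separate ABR models by regimen. The revision history in SAP 12 does not mention bleed intervals either.

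**The concern.** The SAP changes who is summarised, and possibly what is computed, under an unchanged outcome name.

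First, a subject with exactly one bleed has a valid protocol value, namely the whole observation period. The SAP excludes that subject. Inclusion in the summary therefore depends on bleeding at least twice, which is itself an outcome.

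Second, SAP 7.1 does not say whether the average duration is the mean of the observed gaps or observation time divided by count. Two programmers could produce different tables from it. Observed gaps leave out the bleed-free time before the first bleed and after the last one, which the protocol formula counts.

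Third, the CI that the protocol requires is not carried into the SAP text.

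What is at stake is a reported secondary outcome that does not match the protocol's statistical section, with no entry in the place where a reader would look for such a change.

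**Working it through.** The plan states no figure for this outcome, so there is nothing to reproduce. I compare the definitions and then illustrate the size.

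**Definitions.** With T the observation period (OPE) in months and N the number of bleeds:

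- Protocol 13.4.2.1: T/N, defined for N ≥ 1 and undefined at N = 0.
- SAP, restriction only: T/N, kept only if N ≥ 2.
- SAP, gap reading: (last bleed − first bleed)/(N − 1), N ≥ 2.

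Two single-subject cases with T = 12 months:

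- One bleed: the protocol gives 12/1 = 12.0 months; the SAP excludes the subject.
- Two bleeds, at months 5 and 6: the protocol gives 12/2 = 6.0 months; the gap reading gives 6 − 5 = 1.0 month.

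**Assumptions.** From the documents: participation to 100 exposure days "can vary from approximately 3 to 12 months. However, extension of the study duration for individual subjects beyond the 100 EDs may be granted" (Protocol 8.3). Not in the documents, so assumed: mean ABR of 1, 2, 3.5 or 5; counts that are Poisson, or negative binomial with dispersion 1 or 2; bleeds uniform in time given N; and the follow-up mixes, including any value of 36 months. Given N, the subject's mean gap is then T × Beta(N − 1, 2)/(N − 1). The comparator is the median T/N among subjects with at least one bleed.

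**Worked case: ABR 2, dispersion 1, T = 12.** P(N = n) = (1/3)(2/3)^n.

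- Share dropped = P(N=1)/P(N≥1) = (2/9)/(2/3) = 33%.
- Given N ≥ 1, P(N=1) = 1/3 and P(N≤2) = 1/3 + 2/9 = 5/9. The median N is 2, so T/N = 12/2 = 6.0 months.
- Given N ≥ 2, P(N=2) = 1/3 and P(N≤3) = 5/9. The median N is 3, so T/N = 12/3 = 4.0 months.
- The median observed gap is 2.25 months.

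**Range of the share dropped at fixed follow-up.** From 0.034/0.993 = 3% (Poisson, ABR 5, 12 months) to 0.195/0.221 = 88% (Poisson, ABR 1, 3 months).

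**Direction across 156 scenarios, relative to the protocol median:**

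| Follow-up | Scenarios | Gap reading | Restriction alone |
|---|---|---|---|
| Fixed at 3, 6 or 12 months | 36 | shorter in 36, by a factor of 1.30 to 4.34 | shorter 34, unchanged 2 |
| Varying within 3 to 12 months | 72 | shorter in 72, by a factor of 1.39 to 3.99 | shorter 56, unchanged 13, longer 3 |
| Varying up to 36 months | 48 | shorter 45, longer 3 | shorter 31, unchanged 7, longer 10 |
| Total | 156 | shorter 153, longer 3 | shorter 121, unchanged 22, longer 13 |

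**Selected medians in months:**

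| Scenario | Gaps | T/N, N ≥ 2 | T/N, N ≥ 1 |
|---|---|---|---|
| 3 months, dispersion 1, ABR 3.5 | 0.69 | 1.5 | 3.0 |
| 12 months, Poisson, ABR 5 | 1.85 | 2.4 | 2.4 |
| Uniform 3 to 12 months, dispersion 1, ABR 2 | 1.67 | 2.73 | 4.15 |
| 70% at 3 and 30% at 12 months, Poisson, ABR 2 | 2.13 | 4.0 | 3.0 |
| 70% at 3 and 30% at 36 months, Poisson, ABR 2 | 4.39 | 5.14 | 3.27 |

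The last two rows show how the direction can reverse. When many subjects have short follow-up, single-bleed subjects come largely from that group and have short protocol intervals. Removing them leaves mainly long-follow-up subjects. All 13 cases in which the restriction alone lengthens the median are two-point mixes of follow-up; none has uniform follow-up.

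**The case against.** The strongest reply is that the SAP has a protocol basis. Section 11.4 bases the interval on bleed dates, a subject with one bleed has no interval between two bleeds, and even 13.4.2.1 names the quantity as an interval between consecutive episodes. On that view SAP 7.1 resolves an inconsistency within the protocol. The inconsistency is real and needs settling. But 11.4 specifies neither statistic nor population, while 13.4.2.1 gives an explicit formula and a CI, both repeated in the synopsis. Choosing 11.4 would still be a departure from 13.4.2.1 to declare, and it would not remove the required CI.

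Four further points have some force:

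- **T/N adds little beyond ABR.** When T and N cover the same period, T/N in years is the reciprocal of the subject's ABR, which SAP 7.1 already summarises. Observed gaps carry separate information on clustering. This limits the consequence and is a reason to keep the gaps as a supportive summary.
- **The restriction is visible in SAP 7.1.** That is true. What is missing is the entry in SAP 5.7, a formula and a CI.
- **The Output Templates may show a CI.** They are not among the documents, so this cannot be excluded. A CI there would not bring back the single-bleed subjects.
- **The magnitudes are assumed.** They are, and the gap ratios apply only if the average is meant as a mean gap.

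**Conclusion.** The concern holds. As written, SAP 7.1 conditions a listed secondary outcome on having two or more bleeds, leaves its formula open, omits the CI required by Protocol 13.4.2.1, and does not declare this in SAP 5.7. That conclusion rests on the text alone and is firm.

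The numerical effect is uncertain because it depends entirely on the assumed bleed rates, dispersion and follow-up. Under those assumptions the reported median can differ several-fold from the protocol's. It is usually shorter, but neither reading of the SAP guarantees the direction.

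The practical consequence is limited: the outcome is descriptive, and neither the ABR summaries nor the co-primary analyses change. This should be corrected, but it does not threaten the trial's main conclusions.

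**What to change.** In SAP 7.1:

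1. Remove the restriction to subjects with more than one bleed.
2. Define the interval as OPE in months divided by number of bleeds, for every FAS subject with at least one bleed. Use overall OPE with the overall count, and regimen-specific OPE with that regimen's bleeds in tables by regimen.
3. Report the median with the distribution-free 95% CI that SAP 7.1 already names for infusions per bleed. Show beside it the number of subjects with no bleeds. The protocol gives no rule for them, so the SAP must state one.
4. Keep observed gaps, with an explicit formula, as a labelled supportive summary in subjects with two or more bleeds. This serves Protocol 11.4.

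In SAP 5.7, list any departure that remains and state which of Protocol 11.4 and 13.4.2.1 governs. If the sponsor prefers the gap definition as the main summary, the minimum is to give its formula, add the CI, and declare and justify the choice there.

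Optionally, though neither document requires it, add a sensitivity summary that ranks subjects with no bleeds as having the longest intervals, with the median shown as not reached if half or more have none.

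The cost is SAP wording and minor programming. OPE in months (SAP 6.7) and bleeds per subject (SAP 7.1) are already derived, so no new data are needed.
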